### 3.0 Study Design

This will be a single site pilot study. 30 subjects with EPP, defined as medical record documentation of the onset of clinically significant psychotic symptoms within the past ten years, will be enrolled. Prior to randomization (Session 1), subjects will undergo fMRI during EM and RS paradigms. This baseline scan will also include a high-resolution structural sequence for neuronavigation purposes. Then on three separate days each occurring one-week apart, subjects will receive one session of inhibitory (1 Hz) rTMS, one session of excitatory (20 Hz) rTMS, and one sham stimulation session targeting the precuneus. The order of the three interventions will be randomized. Immediately following each rTMS or sham session, subjects will undergo repeat fMRI during EM and RS paradigms. We will also examine the effect of rTMS on EM performance.

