**Low Frequency rTMS:** Low frequency rTMS, or rTMS at 1 Hz or less, is able to produce an inhibitory effect on local brain activity. This has been observed in healthy subject motor corticospinal output. Previous studies have demonstrated that a single session of 1 Hz rTMS is capable of inhibiting local brain activity and modulating distal but related circuitry. This work is in-line with the use of 1 Hz stimulation proposed in this study. **Low Frequency rTMS Protocol:** Subjects will receive one session of low frequency rTMS within the following stimulation parameters: Continuous 20-minute train of 1 Hz rTMS, at 120% of MT, for a total of 1200 pulses. This protocol was shown by Chen et al. (2013) to produce an inhibitory effect on local cortical excitability as well as effects on connectivity of related circuitry.

Both high and low frequency stimulation protocols are within safety limits for rTMS.

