## **13.0 Statistical Considerations**

### **Analyses**

#### *Power Analyses*

In terms of the power to detect a significant effect of precuneus directed rTMS on EM performance or neurocircuitry, there are no known calculations with EPP patients. We plan to enroll 30 subjects and anticipate a 20% drop out rate, thus yielding 24 completers. This is consistent with our previous clinical trial efforts in early phase psychosis populations, including a study of adjunct rTMS for cognitive impairment and negative symptoms. For all planned analyses, a total of 24 subjects in a cross-over design will result in 0.8 power to detect an assumed treatment difference at medium effect size 0.6; using an alpha level of 0.05 and conservatively assumed a within-subject correlation of 0.5. As no previous precuneus rTMS pilot study was available, this standardized effect size of 0.6 is considered to a conservative estimate to detect the significant results.

[figure not shown]

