#### *Statistical Analyses*

[figure not shown]
Intent-to-treat (ITT) analysis will be conducted, and thus all randomized subjects will be included. ITT is the most conservative approach for detecting a treatment effect, because the inclusion of subjects who do not complete the intervention will serve to underestimate rather than overestimate any treatment effect. Sensitivity analyses including a subset analysis using a “completers only” analysis will be performed to test the robustness of the findings. Statistical tests will be performed based on two-sided test at the 5% level of significance.

Descriptive characteristics at baseline will be summarized for the whole sample. For continuous variables, the mean and standard deviation will be presented. For categorical variables, the number and percent will be reported.

Primary analyses: For each subject, change scores in activation of the precuneus (aim 1), functional connectivity (aim 2), and EM performance (aim 3) will be calculated at each treatment by using (post - baseline). We will employ a mixed model for repeated measures ANCOVA, of the general form for each measure:  $change_{ijk} = \mu + \alpha_i + b_{ij} + \gamma_k + \beta X_{ijk} + \tau_d(i, k) + e_{ijk}$ , where  $\mu$  is overall mean;  $\alpha_i$  is the effect of the  $i$ th treatment sequence ( $i = 1, 2, \dots, 6$ );  $b_{ij}$  is the random effect with variance  $\sigma_b^2$  for the  $j$ th subject ( $j = 1, 2, \dots, 24$ ) of the  $i$ th treatment sequence;  $\gamma_k$  is the period effect ( $k = 1, 2, 3$ );  $\beta X$  is the baseline value;  $\tau_d(i, k)$  is the direct effect of the treatment administered in period  $k$  of sequence group  $i$ ; and  $e_{ijk}$  is the random error with variance  $\sigma^2$  for the subject in period  $k$ . Based on this model, we will compare the treatment difference in change score between 1 Hz and Sham as well as 20 Hz and Sham. Under the assumption of missing at random, this mixed effect model will provide the unbiased estimates.

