Secondary analyses: We expect two mediation relations: (1) the treatment affects the connectivity through the activation of the precuneus; and (2) the treatment affects the EM performance through the activation of the precuneus. We use the first mediation as an example. The following 3 equations proposed by Baron and Kenny will be analyzed in order to establish mediation:  $change_{ijk} = \mu + \alpha_i + b_{ij} + \gamma_k + \beta X_{ijk} + \tau_d(i, k) + e_{ijk}$  (1);  $change_{ijk} = \mu + \alpha_i + b_{ij} + \gamma_k + \beta X_{ijk} + \gamma M_{ijk} + \tau_d(i, k) + e_{ijk}$  (2); and  $M_{ijk} = \mu + \alpha_i + b_{ij} + \gamma_k + \beta X_{ijk} + \tau_d(i, k) + e_{ijk}$  (3). Four steps are to be evaluated. First, a significant relation of treatment to the change in connectivity is required in (1). Second, a significant relation of treatment to the change in activation of the precuneus is required in (3). Third, mediator, the change in the activation of the precuneus, must be significantly associated with change in connectivity when both treatment and mediator are controlled as covariates. Fourth, the coefficients of treatment in (1) must be larger (in absolute value) than the coefficients of treatments in (2). If four steps are met, we will consider that the change in activation of the precuneus is mediator of the relationship between treatment and change in connectivity.

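### The four-step mediation rule cannot separate mediation from non-causal variation shared by activation and outcome, and it does not identify direction

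*Combined protocol and SAP*

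**What the plan says.** Section 13.0, Secondary analyses, expects precuneus activation to carry the treatment effect to connectivity and, separately, to EM performance. The stated purpose of the three equations is to establish mediation. The four steps are:

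1. treatment significantly affects the outcome, equation (1);
2. treatment significantly affects activation, equation (3);
3. activation is significantly associated with the outcome given treatment, equation (2);
4. the treatment coefficient is smaller in absolute value in (2) than in (1).

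If all four hold, "we will consider that the change in activation of the precuneus is mediator of the relationship between treatment and change in connectivity".

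Section 3.0 randomises the order of the three conditions. It takes the measurements together: "Immediately following each rTMS or sham session, subjects will undergo repeat fMRI during EM and RS paradigms". All three equations have a random subject intercept and separate, uncorrelated errors. The plan does not say whether the steps apply to each active-sham contrast or to treatment overall. It states no assumption about common causes of activation and outcome, and plans no reversed model and no sensitivity analysis for this conclusion.

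**The concern.** Randomising the order supports a causal reading of steps 1 and 2, but not of step 3. Within a treatment condition, the link between activation and outcome is observational. Anything that moves both on the day (arousal, attention, symptom state, residual motion) creates an association that step 3 cannot tell from a causal path.

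Shared sources are visible in the plan. Under Brain Imaging Analyses, the precuneus sphere is both the activation region and one end of each precuneus connection. For the second mediation, activation is contrasted on correct trials only, and the button presses that define those trials also give EM accuracy (Scene Encoding and Recognition Tasks). In addition, a single mediator slope in a random-intercept model pools within-subject with between-subject association, so stable differences between people can also help step 3 to pass.

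At stake is a statement of mechanism. Section 1.0 says the study will inform later trials on target engagement. The problem is greatest when Aims 1 and 2 succeed, which is when such a statement would most likely be used.

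**Working it through.** **1. The plan's own figure.** Inputs are from Power Analyses and Statistical Analyses: "a total of 24 subjects in a cross-over design will result in 0.8 power", "an assumed treatment difference at medium effect size 0.6", "using an alpha level of 0.05 and conservatively assumed a within-subject correlation of 0.5", "Statistical tests will be performed based on two-sided test at the 5% level of significance".

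- SD of a within-subject difference = √(2(1 − 0.5)) = 1, so the standardised paired difference is 0.6/1 = 0.6.
- Noncentrality = 0.6 × √24 = 2.94. A paired t test gives power 0.804; with the crossover model's 44 df it is 0.820.
- "We plan to enroll 30 subjects and anticipate a 20% drop out rate": 30 × 0.80 = 24.

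The stated 0.8 reproduces for one contrast on one measure. The plan gives no operating characteristics for the mediation rule.

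**2. What the rule sees when there is no mediation.** Within subjects, let M = aT + e_M and Y = cT + e_Y, with no path from M to Y, equal error variances and corr(e_M, e_Y) = r. Regressing Y on T and M then gives a mediator slope of r and a treatment coefficient of c − a·r. With a = c = 0.6:

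- r = 0.3: 0.6 − 0.6 × 0.3 = 0.42. The coefficient shrinks, so step 4 tends to pass.
- r = −0.3: 0.6 + 0.18 = 0.78. The coefficient grows, so step 4 tends to block the declaration.

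**3. How easily step 3 passes.** A within-subject fit has 72 observations − 24 subjects − 2 period − 2 treatment − 1 mediator terms = 43 df. The critical t is 2.017, so a partial correlation of 2.017/√(2.017² + 43) = 0.29 is enough.

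**4. What steps 1 and 2 contribute.** With r = 0, the chance of passing both on the 20 Hz contrast is about 0.820² = 0.67. The simulated value rises to 0.73 at r = 0.7. This caps the rule on that contrast.

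**5. Simulation of all four steps.** Assumptions: 24 completers, 6 sequences, 3 periods; effects 0, −0.6 and +0.6 on both measures; subject and error variances of 0.5 each (correlation 0.5); no M-to-Y path. r is not in the documents and is varied. Ranges span repeated runs. Monte Carlo error is about ±2.5 points at 1,500 trials.

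| r | 20 Hz contrast, random intercept | 20 Hz contrast, within-subject fit | Overall treatment test |
|---|---|---|---|
| 0 | 1.5–2% | 1.5–2% | 2–2.5% |
| 0.2 | 16–17% | 17–18% | 23–25% |
| 0.3 | 31–33% | 35–36% | 45–50% |
| 0.4 | 51% | 54% | 73–77% |
| 0.5 | 64% | 65–67% | 90–93% |
| 0.7 | 73% | 73% | 98–99% |

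Variations:

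- r = −0.2, −0.3, −0.5, −0.7 (within-subject fit): 0.1%, 0%, 0%, 0%, on both readings.
- Effects of ±0.4, r = 0.3–0.7: 12–38% (20 Hz contrast), 36–81% (overall test).
- Effects of ±0.3, r = 0.3–0.7: 5–20% and 19–53%.
- Both contrasts required, effects of ±0.6, r = 0–0.7: 1% to 52%.
- No treatment effect on either measure: at most 2%.
- Adding an equal subject-level correlation at r = 0.3: the overall-test rate rises from 41–45% to 64%, so the session-only figures are not a worst case.

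**6. Roles swapped.** Steps 1 and 2 change places, and with within-subject slopes step 3 tests the same partial correlation. When the rule fired on the 20 Hz contrast at r = 0.3–0.7, the reversed version also fired in 81–100% of trials (random intercept) and 98–100% (within-subject fit). Under simulated true mediation without confounding it fired in 92–100% of declared trials.

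**The case against.** - **The size depends on an unknown.** The residual correlation is not documented and could be negative. Activation is a difference of betas within a run and connectivity is a time-series correlation, so a positive sign cannot be presumed. This stands: no single false-declaration rate can be attached to the rule.
- **Steps 1, 2 and 4 do work.** A reader might infer that the rule tests only whether the two measures vary together within a session. It does not: steps 1 and 2 cap the rate, and step 4 blocks declarations when the shared noise is negative.
- **Shared noise is reduced.** Brain Imaging Analyses includes motion and motion-derivative regressors, outlier exclusion and ANATICOR. Physiological recordings are available for analysis, and connectivity has its own task-free run. The shared-region argument does not reach the EM-performance mediation. All this lessens the problem, but it does not remove arousal, attention or symptom state on the day.
- **The order comes from the design.** The precuneus is the stimulated target, so placing activation first is reasonable. That is an assumption brought to the data, not something the four steps test. The swap result shows that direction is not identified; it does not show that a declaration is false.
- **It is a secondary analysis in a pilot.** True, and section 2.0 words Aim 3 as relationships. The closing sentence of the rule nevertheless goes further than that wording.

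**Conclusion.** The concern holds in this form: meeting the four steps does not establish that activation is the mediator. With true effects of 0.6 on both measures and no mediation, the false-declaration rate on the 20 Hz contrast runs from about 2% at zero residual correlation to 73% at 0.7. It is near 0% for negative correlation, and on the overall-test reading it reaches 98–99%. These figures rest on an assumed correlation and on the plan's effect size applying to both measures; at 0.4 or 0.3 they fall as shown.

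Two stronger readings are not supported. One is that the rule is wrong in some fixed share of trials, such as a third to three quarters: that needs a positive correlation of about 0.3–0.7, which the documents do not give. The other is that the protocol itself describes parallel effects. Section 3.0 says that "a single session of 1 Hz rTMS is capable of inhibiting local brain activity and modulating distal but related circuitry", which is equally compatible with a serial path. Nor does the plan state a null hypothesis for mediation that the rule could be said to violate.

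The 1 Hz-sham and 20 Hz-sham comparisons are unaffected. The change should be made because the conclusion is causal and the correction is cheap.

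**What to change.** In section 13.0, Secondary analyses, replace the closing sentence with:

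> If the four steps are met, the changes in activation and in connectivity (or EM performance) will be reported as associated and consistent with, but not establishing, mediation; the direction is not identified.

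For each of the two mediations, add:

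- the mediator entered as its within-subject deviation, with the subject mean as a separate term;
- the reversed-role model, reported beside the planned one;
- a sensitivity analysis giving the indirect effect over a range of session-level (within-subject) error correlations, negative and positive, with the value at which it becomes zero. Use the same baseline covariates in (1) and (3), so that this value is well defined.

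State also whether the steps apply to each contrast or to treatment overall, since the table shows that this matters.

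The cost is a weaker secondary claim and a little more analysis on data already collected. No extra subjects, scans or visits are needed.

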## 2.0 Specific Aims and Hypothesis

The **first primary aim** is to demonstrate how targeting the precuneus with rTMS impacts functional activation (FA) in individuals with schizophrenia during EM tasks. We predict that, compared to sham stimulation, 1 Hz rTMS will result in decreased FA of the precuneus and 20 Hz rTMS will result in increased FA of the precuneus. The **second primary aim** is to demonstrate how targeting the precuneus with rTMS impacts precuneus functional connectivity (FC) in individuals with schizophrenia. We predict that compared to sham stimulation, FC between the precuneus, the DLPFC, the hippocampus, and the ACC will be decreased in response to 1 Hz rTMS and increased in response to 20 Hz rTMS. The **third primary aim** is to characterize the relationships between EM performance and changes in precuneus functional activation and connectivity. We predict that improved EM performance will be associated with increased precuneus functional activation and connectivity, while poorer EM performance will be associated with decreased precuneus functional activation and connectivity. The **secondary aim** is to characterize how targeting the precuneus with rTMS affects episodic memory performance in individuals with schizophrenia. We predict that compared to sham stimulation, 1 Hz rTMS will impair EM performance and that 20 Hz rTMS will improve EM performance.

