### *Magnetic Resonance Imaging (MRI) Procedures*

MRI will be performed at the IU Center for Neuroimaging using an integrated 45-minute exam, including structural and fMRI. Scans will be completed on a research-dedicated Siemens MAGNETOM Prisma 3T scanner. First, we will conduct a high-resolution 3D magnetization

prepared rapid gradient echo (MPRAGE) scan for individual anatomical reference, comprised of 160 sagittal slices with 1.0x1.0x1.2 mm voxel dimension. Subjects will practice tasks on a personal computer during Visit 1 and prior to the scan at subsequent visits. An MRI-compatible response box will be utilized for tasks, recording reaction time and accuracy. Functional scans will be acquired using T2\*-weighted gradient spin echo-planar imaging (EPI) sequence with TR/TE 1200/29 ms for 54 axial slices and voxel size of 2.5x2.5x2.5 mm. fMRI will employ scene encoding and recognition EM paradigms, shown by our group and others to demonstrate reliable precuneus activation during cognitive functions of interest. We have successfully implemented all tasks in multiple studies of patients with psychosis. A task-free resting state fMRI scan will also be acquired to measure functional connectivity between precuneus and associated structures and circuits.

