#### **Scene Encoding and Recognition Tasks:**

These tasks utilize stimuli and a task design modified from that used by Detre et al. in EM studies in temporal lobe epilepsy. We will be using methods identical those in our previous work. During encoding task, subjects view complex scenes one at a time and are instructed to remember each for later recognition testing (Fig. 3). Images are shown in a block design with interleaved 36-s image and control blocks. Image blocks consist of nine consecutive images, each displayed for 3.5 s, with an inter-stimulus interval (ISI) of 500 ms. A total of 36 scene images are shown. Control blocks consist of a retiled image, repeatedly displayed at the same rate. Subjects do not press buttons during the encoding phase. The recognition task is a separate event-related fMRI paradigm administered immediately after the encoding phase. During the recognition task, subjects are shown the 36 scenes from the encoding phase intermixed with 36 new scenes. These images will be displayed consecutively in a pseudorandomized manner, each for 3.5 s with an ISI of 500 ms. Subjects are instructed to indicate, via button press, whether each displayed image was previously seen (target) or new (foil). Button-press responses are recorded to assess reaction time and accuracy. Task length for each trial is 5:15. Different versions of the scene encoding and recognition EM tasks will be utilized, with order of administration randomized, to mitigate the potential impact of learning effects.

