**Brain Imaging Analyses:** **Aim 1.** Data analysis of the blood-oxygen level-dependent (BOLD) time series will utilize standard preprocessing through the AFNI software package. Standard preprocessing includes motion correction, despiking, detrending, smoothing, and exclusion of signal and motion outlier time points. Each condition's timing will be convolved with a hemodynamic response function to model an ideal response for that condition. General linear modeling will provide a regression coefficient estimate (beta) of the BOLD response to each condition (Target correct; Foil correct; Target incorrect; Foil incorrect). We will also include regressors of no interest for motion and motion derivatives to reduce noise. For our primary analysis, we will create a region of interest (ROI) as a 10-mm radius sphere around our rTMS target in the precuneus. **fMRI Contrast:** Each event type will be modeled separately. Brain activity will be examined by contrasting the estimated beta coefficients for correct trials only (Target correct vs. Foil correct). We will **extract the mean response from this contrast from our precuneus ROI** and evaluate the aim via a mixed model for repeated measures. **Aim 2.** Beyond standard preprocessing, time-series data will be filtered to extract low frequency (< 0.08 hz) BOLD data. The ANATICOR approach (within AFNI) will be used to reduce noise from physiological or hardware sources. ANATICOR utilizes tissue segmentation to control for spatially coherent fluctuations emanating from non-gray matter. Structural regions of interest (ROIs) will be defined on each side with Talairach-based atlases available via AFNI software for the ACC and bilateral middle frontal gyrus, in addition to the spherical precuneus ROI. Visual inspection of ROIs will ensure their correct position. The mean preprocessed time series will be extracted from each ROI, and time-series correlations between ROIs will be calculated. These correlations will be used as the dependent variable in a mixed model for repeated measures ANCOVA, with post-hoc tests as necessary. Supplementary analyses will examine connectivity differences of the precuneus ROI across the entire brain (corrected  $p < .05$ ).

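### Aim 1 predicts lower or higher precuneus activation during EM tasks, but its only measure is an old-minus-new recognition contrast that cancels a shift shared by targets and foils; the encoding run has no planned analysis

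*Combined protocol and SAP*

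**What the plan says.** Section 2.0 sets the first primary aim as showing how precuneus stimulation "impacts functional activation (FA) in individuals with schizophrenia during EM tasks". It predicts that, against sham, "1 Hz rTMS will result in decreased FA of the precuneus and 20 Hz rTMS will result in increased FA of the precuneus".

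Section 6.0 (MRI Procedures) states that "fMRI will employ scene encoding and recognition EM paradigms". The task subsection describes two separate runs:

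- Encoding: "Images are shown in a block design with interleaved 36-s image and control blocks". Control blocks repeat a retiled picture at the same rate.
- Recognition: the 36 encoded scenes (targets) are mixed with 36 new ones (foils). "These images will be displayed consecutively in a pseudorandomized manner, each for 3.5 s with an ISI of 500 ms". No control or null events are described.

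Section 13.0 (Brain Imaging Analyses, Aim 1) estimates a beta for "each condition (Target correct; Foil correct; Target incorrect; Foil incorrect". These event types exist only in the recognition run. It then fixes the contrast: "Brain activity will be examined by contrasting the estimated beta coefficients for correct trials only (Target correct vs. Foil correct". The plan will "extract the mean response from this contrast from our precuneus ROI" and carry that value into the mixed model. No other Aim 1 outcome is named, and no section gives the encoding run a regressor, contrast or outcome. The one supplementary imaging analysis, across the whole brain, concerns connectivity under Aim 2.

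**The concern.** The aim speaks of activation going down or up. The measure is the difference between two memory conditions. Section 1.0 and the stimulation protocols in Section 3.0 describe the mechanism as a change in local cortical excitability. Such a change could plausibly alter the response to old and new scenes alike, and the part that they share drops out of the contrast.

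At stake is what Aim 1 can conclude. A null contrast could be read as no change in precuneus activation when only the old/new difference was tested. The same quantity appears to serve as the mediator in the secondary analyses, where a significant treatment effect on precuneus activation is one of the four required steps. An effect missed in Aim 1 would then also stop both mediation analyses. Meanwhile, the one task run with a non-memory control condition goes unanalysed.

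**Working it through.** **Inputs.** From Sections 3.0 (Sample Size) and 13.0 (Power Analyses): 24 completers, standardized difference 0.6, alpha 0.05, within-subject correlation 0.5, power 0.8. Tests are two-sided (Statistical Analyses). From the task subsection of 6.0: 36 targets and 36 foils, 3.5 s each with a 0.5 s interval; nine images per 36-s block; task length 5:15. Betas, gain and the shared fraction are assumptions.

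**1. The plan's own figure.** For a within-subject comparison, dz = 0.6 / sqrt(2 × (1 − 0.5)) = 0.6. A paired t-test with n = 24 and 23 df gives power 0.804. The stated 0.8 reproduces, and 24 / (1 − 0.2) = 30 enrolled. The sample-size arithmetic is not in question.

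**2. What the contrast keeps.** Let T and F be the betas for correct targets and correct foils. The baseline scan is the same for all three treatments, so it cancels from treatment differences in change score; only the post-stimulation contrasts matter.

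- Additive shift s on both: (T + s) − (F + s) = T − F. None of the shift is seen. With assumed T = 1.0 and F = 0.8, adding −0.3, 0 or +0.3 to both leaves 0.20 each time.
- Proportional gain on both: the contrast becomes gain × (T − F). With the same betas and a gain of 1.3, it moves from 0.20 to 0.26, while the mean response moves from 0.90 to 1.17. This shows shrinkage in raw units only; without the SD of each measure it says nothing about relative detectability.
- Effect on targets only: passed on in full.

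**3. Consequence for power.** Let f be the fraction of a 0.6 SD shift that is specific to targets, and assume that the contrast has the planning SD and correlation. The effect on the contrast is f × 0.6.

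| f | Effect on contrast (SD) | Power, n = 24 |
|---|---|---|
| 0 | 0 | 0.05 (simulated 0.052) |
| 0.25 | 0.15 | 0.11 |
| 0.50 | 0.30 | 0.29 |
| 0.75 | 0.45 | 0.56 |
| 1 | 0.60 | 0.80 |

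**4. Could the recognition run supply the overall response?** Its stimuli take 72 × (3.5 + 0.5) = 288 s. If 5:15 (315 s) is the length of that run, at most 315 − 288 = 27 s, about 9%, is free of stimuli. The text does not say which run the length describes. Encoding has 36 / 9 = 4 image blocks, or 4 × 36 = 144 s; with four control blocks (number assumed) it also comes to 288 s.

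A design-matrix check assumed a canonical haemodynamic response, white noise, 75% accuracy and 315-s runs. The mean recognition response against implicit baseline had a standard error of about 0.40 to 0.43 noise units, against about 0.15 for encoding image versus control. Single-condition recognition betas are therefore available but imprecise.

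**5. Is encoding scanned at every visit?** Attachment 1 lists EM-task MRI at Visits 1 to 4 without separating the runs. Recognition tests scenes from the encoding phase just before it, and Section 6.0 names both paradigms for fMRI. Four encoding runs per subject is thus an inference, though a firm one: up to 4 × 30 = 120 runs.

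**The case against.** The strongest defence is that the contrast was chosen for a reason. Section 1.0 justifies the precuneus by its part in retrieval search, verification and familiarity judgements. Correct old against correct new tests that function directly, whereas a scene-viewing contrast is less specific. This stands, and it is why the contrast should remain primary.

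The cancellation argument also depends on the shape of the effect. The documents speak of excitability, not of an equal shift for targets and foils. This stands too: the loss is conditional.

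Four stronger readings are tempting, but the documents do not support them:

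- A reader might infer that the recognition run cannot yield an overall response. The planned model estimates a beta for each event type; these are unused as outcomes and would be imprecise, but they exist.
- A reader might infer that target engagement rests on this contrast alone. Section 1.0 also lists connectivity and EM performance, and Aim 2's resting-state connectivity does not use it.
- A reader might take encoding image minus control as an absolute activation level. It is also a difference: (I + s) − (C + s) = I − C. Its advantage is a non-memory comparison condition.
- A reader might call the encoding scans wasted. They are needed in any case, because encoding creates the targets.

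**Conclusion.** The point holds as a mismatch between the Aim 1 prediction and its single measure. None of an additive shift common to targets and foils reaches the outcome, and a common proportional gain reaches it only through the old/new difference. A null result therefore cannot be read as unchanged precuneus activation, and a positive result is an effect on the old/new retrieval response.

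The practical loss is not known. The power range of 0.05 to 0.80 rests on an assumed target-specific fraction and on carrying the planning SD and correlation over to the contrast. A reader might infer that the trial will miss a real effect of stimulation; that follows only if the effect is largely shared by the two event types, which no section states. The use of the same contrast as mediator is the natural reading of Section 13.0, but is not spelled out there. This is a worthwhile, cheap improvement rather than a fatal flaw.

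**What to change.** In Section 13.0, Brain Imaging Analyses, Aim 1:

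1. Keep Target correct minus Foil correct in the precuneus region as the sole primary Aim 1 outcome, and word its conclusion as an effect on the old/new retrieval response.
2. Add a pre-specified secondary, supporting outcome: the mean image-minus-control beta from the encoding run, in the same precuneus region and the same mixed model (1 Hz vs sham, 20 Hz vs sham).
3. Describe that outcome as scene-encoding activation relative to a non-memory visual control, and state that it cancels any effect common to image and control blocks.

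The cost is one extra first-level model per existing scan and one extra mixed-model fit, with no new scans or visits. The downside is two additional secondary comparisons, which cannot on their own confirm the primary hypothesis; the plan should say so.
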